#### **15.1.1. INJECTION SITE REACTION DIARY RESULTS**

Injection site reactions captured on the diary card will be listed by subject and visit and include the AE number for reactions that are reported as AEs. Subjects were requested to complete the diary card for the first 3 days. If symptoms were still present after the 3 days, subjects would complete the diary until the symptoms had totally disappeared.

These data will be summarised as frequency counts for each grade of reaction parameter, by visit for the ITT population. In the event of more than one response per reaction parameter per visit per patient, only the most severe occurrence for each injection site reaction for each subject per visit will be counted.

## **15.2. LABORATORY EVALUATIONS**

Blood samples for haematology, and biochemistry and urine samples for urinalysis will be collected and eCRF entries made for the collection date/time and reason for non-collection if applicable. The

---

Document:	ATX_GD_59 Final 1.0 SAP 28FEB2018.docx	Version Number:	Final 1.0
Author:	[name]	Version Date:	28FEB2018

Template No: CS\_TP\_BS016 Revision 4  
Effective Date: 01Apr2016

Reference: CS\_WI\_BS005

Investigator is to review the laboratory report promptly, document this review, and record any clinically relevant changes occurring during the study on the Adverse Events eCRF.

Laboratory safety assessments will be assayed by Q2 Solutions Central Laboratory.

Results from the central laboratory will be included in the reporting of this study for Haematology, Biochemistry and Urinalysis. For a list of the clinical laboratory assessments to be included in the outputs together with their conversion factor to Système International (SI) units, refer to Appendix 3: Conversion Factors to Système International (SI) Units of this SAP.

Presentations will use SI units.

Quantitative laboratory measurements reported as “< X”, i.e. below the lower limit of quantification (BLQ), or “> X”, i.e. above the upper limit of quantification (ULOQ), will be converted to X for the purpose of quantitative summaries, but will be presented as recorded, i.e. as “< X” or “> X” in the by-subject listings.

The following summaries will be provided for laboratory data for the ITT population:

- Descriptive statistics (observed and change from baseline) will be presented for quantitative measurements of Haematology, Biochemistry and Urinalysis laboratory results at baseline and the scheduled protocol post-baseline visits (excluding FT3, FT4 and TSH that will be summarised separately under efficacy).
- Frequency count for markedly abnormal results will be presented for quantitative measurements of Haematology, Biochemistry and Urinalysis laboratory results by visit and dose level (excluding FT3, FT4 and TSH that will be summarised separately under efficacy).
- Shift from baseline to each scheduled protocol post-baseline visit for quantitative measurements of Haematology and Biochemistry laboratory results categorised according to normal reference range as low, normal or high. Markedly low and markedly high results will be included in low and high counts respectively. For the shift the percentage (%) of subjects in each category calculated relative to the total number of subjects in the relevant analysis population with assessments available at baseline and the relevant post-baseline visit per laboratory parameter (excluding FT3, FT4 and TSH that will be summarised separately under efficacy).
- Listing of individual subjects with clinical laboratory results outside of normal range and markedly abnormal results, including their change from baseline (including FT3, FT4 and TSH). Only out of range results that are not also outside markedly abnormal ranges will be included in the normal range listing. Assessments post administration of anti-thyroid drugs will be flagged.

---

Document: ATX\_GD\_59 Final 1.0 SAP 28FEB2018.docx  
Author: [name]

Version Number: Final 1.0  
Version Date: 28FEB2018

Template No: CS\_TP\_BS016 Revision 4  
Effective Date: 01Apr2016

Reference: CS\_WI\_BS005

Copyright © 2009, 2010, 2012, 2016 Quintiles Transnational Corp. All rights reserved.  
The contents of this document are confidential and proprietary to Quintiles Transnational Corp. Unauthorized use, disclosure or reproduction is strictly prohibited.

The following laboratory data will be presented in by-subject listings for the Study population:

- Serum and urine pregnancy test results.
- Reference ranges per laboratory parameter, sex and age range (including FT3, FT4 and TSH).
- Markedly abnormal ranges per laboratory parameter, sex, visit and age range (including FT3 and FT4).
- All clinical laboratory results including change from baseline values will be presented by site/subject, dose level and date/time of assessment, including scheduled, unscheduled and ET visits. Listings will include flags for outside of reference range, markedly abnormal results and will identify the values that are regarded as baseline values (excluding FT3, FT4 and TSH that will be listed separately under efficacy).
- Urinalysis results will be listed for continuous and categorical (e.g. positive/negative) data. Continuous data will be presented as above.
- Laboratory results for laboratory parameters not listed in the protocol will be listed only and will not appear in any summary tables.
- For all listings, all visits will be listed where protocol-specified tests are to be done. The accession number and reason if not done will also be listed. Assessments post administration of anti-thyroid drugs will be flagged.

#### **15.2.1. LABORATORY REFERENCE RANGES AND MARKEDLY ABNORMAL CRITERIA**

Quantitative laboratory measurements will be compared with the relevant laboratory reference ranges in SI units and categorised as:

- Low: Below the lower limit of the laboratory reference range.
- Normal: Within the laboratory reference range (upper and lower limit included).
- High: Above the upper limit of the laboratory reference range.
- Markedly Low: Below the lower limit of the laboratory markedly abnormal reference range.
- Markedly High: Above the upper limit of the laboratory markedly abnormal reference range.

---

Document: ATX\_GD\_59 Final 1.0 SAP 28FEB2018.docx  
Author: [name]

Version Number: Final 1.0  
Version Date: 28FEB2018

Template No: CS\_TP\_BS016 Revision 4  
Effective Date: 01Apr2016

Reference: CS\_WI\_BS005

Copyright © 2009, 2010, 2012, 2016 Quintiles Transnational Corp. All rights reserved.  
The contents of this document are confidential and proprietary to Quintiles Transnational Corp. Unauthorized use, disclosure or reproduction is strictly prohibited.

## 15.3. VITAL SIGNS

Subjects will be observed in the clinic for at least two hours after administration of the study drug. Vital signs will be recorded at screening, and on each dosing day, pre-dose, then at 15 minute intervals for the first hour and 30 minute intervals for the second hour, and at Week 22 and 30 follow-up visits and at ET, after the subject has been sitting quietly for at least 5 minutes.

The following vital signs measurements will be reported for this study:

- Sitting SBP (mmHg)
- Sitting DBP (mmHg)
- Sitting Heart Rate (bpm)
- Oral Body Temperature (°C)
- Respiratory Rate (breaths/min)
- Weight (kg) (Note BMI is calculated at Screening only).

The following summaries will be provided for the vital sign data for the ITT population:

- Descriptive statistics (observed, change from baseline and change from pre-dose to each post-dose time point for each parameter except weight) will be presented for each vital sign parameter at baseline, pre-dose and at each scheduled post-baseline visit.

The following vital signs listing will be presented for the Study population:

- Vital signs measurements (including change from baseline and change from pre-dose to each post-dose time point for each parameter except weight) by site, subject, date and time.
- Baseline values and trigger values will be flagged in the listings for the following:
  - o Weight decrease from baseline by > 5 kg
  - o Heart rate > 120 bpm
- Assessments post administration of anti-thyroid drugs will be flagged.

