6. Subject requires treatments prohibited by the exclusion criteria or the protocol.
7. Subject demonstrates a robust and increasing positive response in the anti-drug anti-body assay accompanied by clinical signs of an adverse immune response to either peptide in ATX-GD-59. These may be unexplained chills, fever or flu like symptoms following treatment with ATX-GD-59.
8. Subject becomes pregnant.

Management of thyrotoxicosis during the study

- Symptomatic patients may be treated with propranolol (up to 160mg per day) adjusted to control tachycardia or other symptoms. If alternative beta-adrenergic receptor blockade is required, this must be agreed with the study medical monitor.
- If there is a contraindication to using a beta blocker (e.g., asthma) then rate limiting calcium channel blockers (e.g. Diltiazem MR 120 to 240mg daily) may be used instead. This must also be agreed with the study medical monitor.

Administration of Anti Thyroid Drug's during the study is indicated in the following instances:

- A subject has trigger levels of free T3 (>20pM) and/or free T4 (>45pM) on 2 consecutive scheduled or unscheduled visits.
- Continued weight loss >5kg from baseline (Study Day 1).
- Persistent tachycardia >120bpm.
- Significant cardiac event that would require urgent treatment of thyrotoxicosis.
- If the investigator or treating physician considers that it is appropriate to administer anti-thyroid drugs at any point during the study.

Duration of treatment:

The trial consists of a screening visit, a dosing period of 18 weeks, an efficacy assessment after 4 weeks (post final dose) and a follow-up period of 8 weeks.

Dose and mode of administration:

ATX-GD-59 is a lyophilised equimolar mixture of two peptides reconstituted at the clinic to provide one of two different concentrations, depending on dose, for injection prior to intradermal injection.

Dose Strengths: 4mg/ml and 0.5mg/ml total peptide content when reconstituted in water for injection and 0.9% saline respectively.

Safety monitoring and analysis:

Subjects will be observed in the clinic for at least two hours after administration of the study drug and vital signs will be recorded at 15 minute intervals for the first hour and 30 minute intervals for the second hour. If the subject is well (in the opinion of the Investigator), they will then be allowed to leave the clinic. A contact card with an emergency telephone number will be provided to each subject.

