## 3. STUDY OBJECTIVES

### 3.1. PRIMARY OBJECTIVE

The primary objective is to evaluate whether ATX-GD-59 administration every two weeks by intradermal injection is safe and well tolerated in male and female subjects with Graves' disease, not currently treated with anti-thyroid therapy.

Safety endpoints, that will be evaluated on an ongoing basis up to Week 22 (i.e., 28 days post last study medication dose), are:

- Injection site reactions as reported by the subjects in the diary card.
- Occurrence of treatment related Adverse Events (AEs), Serious Adverse Events (SAEs), and laboratory abnormalities compared to baseline.
- Results from the physical examination, and vital signs (reported on an ongoing basis and compared to baseline).
- Early withdrawal and reasons for early withdrawal from treatment and/or the study.

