#### 5.4.3. ANTI-THYROID DRUG POPULATION

A third analysis population, the anti-thyroid drug population, is defined as any ITT subject taking anti-thyroid drugs at any time post first dose of ATX-GD-59 to the Week 22 visit.

Efficacy parameters will be summarised for the anti-thyroid drug population provided that it differs from the ITT population by at least one subject and is at least 50% of the ITT population.

All data will be listed for subjects in the anti-thyroid drug population, however, only data up to the time point of dosing with anti-thyroid drugs will be included in summary tables of efficacy (TSHR antibodies and thyroid function tests for subjects in the anti-thyroid drug population). Additionally, visits post administration of anti-thyroid drugs in these subjects will be flagged in all by-visit listings of efficacy and safety data except diary card recordings of injection site reactions, and listings of exploratory efficacy parameter data (B set).

---

Document: ATX\_GD\_59 Final 1.0 SAP 28FEB2018.docx  
Author: [name]

Version Number: Final 1.0  
Version Date: 28FEB2018

Template No: CS\_TP\_BS016 Revision 4  
Effective Date: 01Apr2016

Reference: CS\_WI\_BS005

Copyright © 2009, 2010, 2012, 2016 Quintiles Transnational Corp. All rights reserved.  
The contents of this document are confidential and proprietary to Quintiles Transnational Corp. Unauthorized use, disclosure or reproduction is strictly prohibited.

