## **7. STATISTICAL CONSIDERATIONS**

### **7.1. ADJUSTMENTS FOR COVARIATES AND FACTORS TO BE INCLUDED IN ANALYSES**

Not applicable, as no adjustment for covariates and factors will be done for this study.

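### At each visit the heart-rate and RR summaries mix subjects on and off permitted rate-lowering drugs, unflagged, so they can understate worsening

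*SAP*

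**What the plan says.** SAP 3.1 lists among the safety endpoints of the primary objective: "Results from the physical examination, and vital signs (reported on an ongoing basis and compared to baseline". SAP 15.3 includes sitting heart rate and plans, for the ITT population at each scheduled visit, "Descriptive statistics (observed, change from baseline and change from pre-dose to each post-dose time point for each parameter except weight". SAP 15.4 gives similar summaries for ECG intervals, including RR.

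The protocol synopsis, under management of thyrotoxicosis, states: "Symptomatic patients may be treated with propranolol (up to 160mg per day) adjusted to control tachycardia or other symptoms". Where a beta blocker is contraindicated, "rate limiting calcium channel blockers (e.g. Diltiazem MR 120 to 240mg daily) may be used instead".

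Anti-thyroid drugs are the only added treatment tied to these data. In the vital-sign and ECG listings, "Assessments post administration of anti-thyroid drugs will be flagged". For the anti-thyroid drug population, SAP 5.4.3 adds that "only data up to the time point of dosing with anti-thyroid drugs will be included in summary tables of efficacy". SAP 7.1 says "no adjustment for covariates and factors will be done for this study", and SAP 7.5 rules out subgroup analyses.

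**The concern.** Subjects enter hyperthyroid and off anti-thyroid drugs, and there is no control group, so the course of heart rate over visits is one of the objective signs of whether they got worse on ATX-GD-59. A permitted treatment can be started and adjusted because of that same variable. Subjects with a rising heart rate are more likely to start it. Their later values then combine the course of the disease with the drug's lowering of heart rate, and they are averaged with subjects not on such a drug. A mean change near zero could be read as no worsening when part of it reflects treatment of worsening. The listing flag for heart rate above 120 bpm and the RR summary are exposed in the same way.

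The SAP already accepts the principle for anti-thyroid drugs but does not apply it to the permitted drugs that act directly on heart rate.

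**Working it through.** **Is the link made anywhere?** The documents give no heart-rate figure to reproduce, so the first check is of the text.

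- SAP 15.3 and 15.4: no exclusion, split or flag for beta blockers or calcium channel blockers.
- SAP 12: a drug counts as concomitant if it started or stopped in the period or is ongoing, and a subject counts once per drug name per period. Continued use and a new start look the same, and dose increases do not show.
- SAP 6.2: baseline is the last value before first dose. The eligibility criteria in the protocol synopsis do not exclude rate-lowering drugs, so some subjects may already be on one at baseline.

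No planned table described in the SAP shows who started such a drug after first dose.

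**How large could the effect be?** From the protocol synopsis: about 12 subjects completing and about 15 dosed. Assumed, because the documents give none: rise without the drug R, drug lowering B (15 to 25 bpm) and number treated k.

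*Only k of N worsen, and all k are treated.* Mean without treatment = kR/N. Mean shown = k(R - B)/N. With N = 12, k = 4, R = 20:

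- without treatment: 4 × 20 / 12 = +6.7 bpm
- B = 15: 4 × 5 / 12 = +1.7 bpm
- B = 20: 0.0 bpm
- B = 25: 4 × (-5) / 12 = -1.7 bpm

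Other inputs, same range of B:

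| N | k | R | Without treatment | Shown |
|---|---|---|---|---|
| 12 | 2 | 20 | +3.3 | +0.8 to -0.8 |
| 12 | 6 | 20 | +10.0 | +2.5 to -2.5 |
| 12 | 4 | 30 | +10.0 | +5.0 to +1.7 |
| 15 | 4 | 20 | +5.3 | +1.3 to -1.3 |

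*All N rise by R, and k are treated.* Mean shown = R - (k/N)B, which is zero at k = NR/B. With N = 12 and R = 10, that is 8 subjects at B = 15, 6 at B = 20 and 4.8 at B = 25. With N = 15, k = 5 and R = 15, the mean shown is 15 - B/3, or +10.0 to +6.7 bpm: reduced, not removed.

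**What would each remedy show in the 4-of-12 case?** A table limited to visits before a start keeps only the 8 stable subjects once the 4 have started, and shows 0 bpm. A count of starters with their last change before the start shows 4 subjects at +20 bpm, provided an assessment caught the rise before the drug began.

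**The case against.** The tables are by scheduled visit. A reader might infer that visits are pooled, but SAP 15.3 does not average across them. The mixing is of subjects on and off drug within a visit, and of earlier and later values along each subject's series.

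A reader might also infer that symptomatic treatment simply cancels a general rise. For instance, 10 of 15 subjects at +15 bpm and 5 at -30 bpm give a mean of (150 - 150)/15 = 0. If those 5 would otherwise have risen by 15 bpm too, the drug must have lowered heart rate by 45 bpm. SAP 6.6 also requires median, SD and range: the median would be +15 and the SD √(6750/14), about 22, which plainly shows two groups. That objection stands for this pattern. It does not cover the 4-of-12 case: with the other 8 at zero, the median is 0 with or without treatment, and the maximum falls from +20 to +5 or 0.

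Nor do the documents support saying that every start is triggered by heart rate, or that the bias always runs towards no harm. The protocol also allows propranolol for other symptoms, and stopping or reducing a drug already in use could raise heart rate.

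Worsening can show elsewhere: FT3 and FT4 changes, shifts and markedly high counts (SAP 14.1.3.3), the weight flag (SAP 15.3), and adverse events with a separate listing of Graves' symptoms (SAP 15.1). Medications are listed with indication and vital signs with date and time, so about 15 subjects could be matched by hand. Everything is descriptive, and no decision rule uses mean heart rate. All of this limits the severity, but none of it is a planned output linking drug starts to heart rate.

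The table shells and the full protocol section on vital signs were not available.

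**Conclusion.** The point holds as a reporting weakness of minor to moderate weight. The planned heart-rate and RR summaries cannot distinguish absence of worsening from worsening that was treated, and neither can the flag above 120 bpm. In the 4-of-12 illustration a mean rise of 6.7 bpm appears as +1.7 to -1.7 bpm. This rests on assumed numbers of users, rises and drug effects, and on treatment going mainly to those who worsen. Where all subjects rise and few are treated, the rise is reduced but remains visible. The documents do not show that masking will occur, only that the planned tables could not reveal it.

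**What to change.** Amend SAP 15.3 and 15.4 before database lock:

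1. From the concomitant-medication dates, derive a per-visit flag for a beta blocker or rate-limiting calcium channel blocker started after first dose. Add stops and dose changes if the eCRF records them, which the documents available do not show. Handle use already present at baseline as a separate category. Show the flag in the listings beside the anti-thyroid drug flag.
2. Tabulate the number of subjects who started such a drug after first dose, with their change from baseline in heart rate at the last assessment before the start.
3. Keep the all-subject by-visit table, and add the same heart-rate and RR summary split by whether the subject is on a newly started rate-lowering drug.

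Do not present a table limited to visits before the start on its own: it removes the subjects who worsened.

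The cost is SAP wording, one derived flag, one count and one repeated summary, with small numbers in each part of the split. The start dates are already collected. Clinical management is unchanged.

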## 15.4. ELECTROCARDIOGRAM EVALUATIONS

12-lead ECG results obtained at the investigative site, and will be entered into the eCRF by site staff, at screening, pre-dose and post dose, Week 22 and at ET.

The following ECG parameters will be reported for this study:

- RR (heart rate variability) Interval (msec)
- PR (period that extends from the beginning of the P wave until the beginning of the QRS complex) Interval (msec)
- QRS (onset of ventricular depolarisation) Interval (msec)
- QT (total duration of ventricular depolarisation) Interval (msec)
- QTcB (Bazett's correction formula) Interval (msec)

Overall assessment of 12-lead as per Investigator's judgment of clinical significance:

- Normal
- Abnormal, Not Clinically Significant (NCS)
- Abnormal, Clinically Significant (CS)

The following summaries will be provided for the ECG interval data for the ITT population:

- Descriptive statistics (observed, change from baseline and change from pre-dose to each post-dose time point) will be presented for each ECG parameter at baseline and at each scheduled post-baseline visit.

The following ECG data will be presented in by-subject listings for the Study population:

- 12-Lead ECG interval assessment results, including change from baseline and change from pre-dose to each post-dose time point for each ECG parameter.
- 12-Lead ECG Interpretations (investigator's judgement).
- Assessments post administration of anti-thyroid drugs will be flagged.

---

Document: ATX\_GD\_59 Final 1.0 SAP 28FEB2018.docx  
Author: [name]

Version Number: Final 1.0  
Version Date: 28FEB2018

Template No: CS\_TP\_BS016 Revision 4  
Effective Date: 01Apr2016

Reference: CS\_WI\_BS005

Copyright © 2009, 2010, 2012, 2016 Quintiles Transnational Corp. All rights reserved.  
The contents of this document are confidential and proprietary to Quintiles Transnational Corp. Unauthorized use, disclosure or reproduction is strictly prohibited.

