Inclusion criteria

1. A diagnosis of Graves' disease as assessed by a physician from clinical and laboratory findings and not receiving anti-thyroid therapy.
2. Quantifiable levels of TSHR antibodies.
3. Raised levels of free T3 and/or free T4 (not exceeding 15 pmol/L and 35 pmol/L respectively) including undetectable levels of thyroid stimulating hormone.
4. HLA-DRB1*15, HLA DRB1*03 and or HLA DRB1*04 positive.
5. Age 18 – 65 years inclusive at the time of informed consent.
6. The subject must be willing and able to give written informed consent and must be willing to comply with protocol assessments/procedures.
7. Male subjects must be sterile (biologically or surgically) or commit to the use of a reliable method of birth control for the duration of the study until at least 90 days after the last dose of ATX-GD-59.
8. Female subjects of child bearing potential must:
 - neither be pregnant nor breast-feeding, nor attempting to conceive, and
 - use a highly effective method of contraception as defined below, throughout the entire duration of the study and for at least 90 days after the last dose of ATX-GD-59.

A serum pregnancy test will be performed at the screening visit in women of child bearing potential. Thereafter urine pregnancy tests will be performed. A positive result will exclude the woman from the study immediately.

A highly effective method of contraception is defined as those which result in a low failure rate when used consistently and correctly such as implants, injectable, combined oral contraceptives, some Intrauterine Devices (IUDs), unless post-menopausal or surgically sterilized. Barrier forms of contraception are considered appropriate when used in combination with one of the above methods.

Exclusion criteria

1. Subjects who are pregnant or breastfeeding and/or subjects in the post-partum period.
2. A known history of, or hypersensitivity reactions that in the opinion of the investigator would exclude the subjects' participation in the study.
3. Treatment with any Anti-Thyroid Drugs e.g. carbimazole within the previous 3 months prior to Study Day 1.
4. Previous treatment with radioiodine or (partial or complete) thyroidectomy.
5. Signs of moderate or severe orbitopathy including optic nerve compression requiring steroids and/or a clinical activity score >3.
6. Large and compressive goitres causing localised symptoms such as difficulty swallowing or breathing.

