Subjects will be given diaries to take home to record injection site reactions for at least 24 hours after the study drug injection.

The first four subjects will be recruited sequentially with a minimum of 48 hours between the first dose of each subject. Individual subject safety data will be reviewed by the Investigator and the Sponsor or Sponsor's representative after the first dose of ATX-GD-59 and thereafter between the second (week 10) and third (week 12) 800 µg doses. Dosing of the remaining subjects will only commence once the first subject has received the second dose (week 2) 50 µg and there are no safety concerns identified.

For the first 5 subjects, the combined individual subject safety data will be reviewed by the Investigator and the Sponsor or Sponsor's representative after the second 800 µg dose (week 10) and prior to the third (week 12) 800µg dose.

The combined safety data for the first 5 subjects will be subject to interim review by a Data Monitoring Committee (DMC) after the last dose of 800 µg (week 18) has been administered.

The following will be presented to the DMC in a listing form:

- Summary vital signs.

- Summary ECG data- heart rate, PR interval, QRS width, QT interval and QTc interval.
- Clinical Laboratory data. Out of range values will be flagged in the data listings and a list of markedly abnormal values will be presented.
- Demographic data.
- Safety data, including all adverse events.

The DMC may request additional information as required.

Should safety concerns be identified, a decision may be taken to halt the trial. The DMC may convene at any point during the trial.

All adverse events will be coded using the MedDRA (Medical Dictionary for Regulatory Activities) drug dictionary. Adverse events will be listed and tabulated with simple analyses. Adverse events that occur intermittently will be reported as separate events.

Primary Objective

The primary endpoint of this study is a safety assessment to ensure, first of all, that the exposure to the study drug by the intradermal dose route will not harm a population affected by Graves' disease.

Safety endpoints, which will be evaluated on an ongoing basis **up to Week 22**, are:

- Injection site reactions as reported by the subjects in the diary card.
- Occurrence of treatment related adverse events (Adverse Events), Serious Adverse Events, and laboratory abnormalities compared to baseline.

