### 6.2. BASELINE

Unless otherwise specified, baseline is defined as the last available assessment (scheduled or unscheduled) prior to the first administration of study drug. In the case where the last non-missing measurement prior to first administration of study drug and the reference start date coincide, that measurement will be considered baseline.

Baseline and at each scheduled post-baseline visit as well as separately for multiple assessments within a visit, change from pre-dose to each post-dose assessment will also be evaluated.

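### Bazett is the only QT correction planned, although subjects are hyperthyroid at baseline and heart rate may change on study, so change in QTcB can include a rate-correction artefact

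*SAP*

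**What the plan says.** SAP section 15.4 names five ECG parameters. Three matter here: "RR (heart rate variability) Interval (msec"), "QT (total duration of ventricular depolarisation) Interval (msec") and "QTcB (Bazett's correction formula) Interval (msec"). No other correction is listed, and no categorical QTc summary or heart-rate-adjusted analysis is planned. Section 7.1 rules out covariate adjustment throughout.

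All five parameters get the same treatment in the ITT population: "Descriptive statistics (observed, change from baseline and change from pre-dose to each post-dose time point) will be presented for each ECG parameter". They are also listed by subject. Section 15.3 summarises and lists sitting heart rate.

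Under SAP section 6.2, "baseline is defined as the last available assessment (scheduled or unscheduled) prior to the first administration of study drug". The protocol synopsis requires at entry "Raised levels of free T3 and/or free T4 (not exceeding 15 pmol/L and 35 pmol/L respectively) including undetectable levels of thyroid stimulating hormone", so the baseline ECG is recorded in subjects selected as hyperthyroid and not on anti-thyroid drugs.

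The synopsis then provides for treatment that can alter heart rate: "Symptomatic patients may be treated with propranolol (up to 160mg per day) adjusted to control tachycardia or other symptoms". A rate-limiting calcium channel blocker may replace the beta-blocker, and anti-thyroid drugs may be started under stated conditions, one of which is persistent tachycardia above 120 bpm. The effect of study drug on free T3, free T4 and TSH is a secondary objective. SAP section 4.1 states that there is no control group.

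**The concern.** A rate correction is meant to make QT values comparable across heart rates. Bazett divides by the square root of RR. If the true dependence of QT on RR is weaker than that, QTcB reads too high at fast rates, and it falls when heart rate falls even though repolarisation has not changed.

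This trial has several routes to a heart-rate shift between baseline and later visits: a beta-blocker or calcium channel blocker, an anti-thyroid drug, or an effect of study drug on thyroid hormone. A slowing heart could make QTcB appear to shorten and hide a real prolongation. A quickening heart could produce an apparent prolongation. Without a concurrent control arm, no comparison shows how much of a mean QTcB change is due to rate.

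Visits after anti-thyroid drugs are started also appear to stay in the ECG summaries. Section 5.4.3 removes such data from the efficacy summary tables, whereas section 15.4 only flags them in listings.

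**Working it through.** The documents give no QTc figure to reproduce, so the check is a direct model of the correction.

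**From the documents:** Bazett is the only correction; QT and RR are collected in msec; baseline precedes the first dose.

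**Assumed, not in the documents:** a corrected QT of 400 ms at 60 bpm; the heart rates below; a QT-RR exponent *b* between 1/4 and 1/2; no true QT effect unless stated.

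**Formulas.** RR = 60/HR in seconds and QT = 400 × RR^b. Then QTcB = QT/RR^(1/2) = 400 × RR^(b − 1/2).

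**Step 1. Heart rate falls from 110 to 75 bpm.** RR goes from 60/110 = 0.545 s to 60/75 = 0.800 s. Differences are taken before rounding.

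| Exponent b | QTcB at 110 bpm (ms) | QTcB at 75 bpm (ms) | Spurious change (ms) |
|---|---|---|---|
| 1/2 | 400.0 | 400.0 | 0 |
| 0.40 | 425.0 | 409.0 | -16.0 |
| 1/3 | 442.5 | 415.2 | -27.4 |
| 1/4 | 465.4 | 422.9 | -42.5 |

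**Step 2. Other rate changes.** For 100 to 80 bpm the spurious change is 0, -9.3, -15.9 and -24.7 ms in the same order of exponents. For a rise from 90 to 120 bpm it is 0, +12.2, +21.0 and +33.0 ms.

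**Step 3. Masking.** Take b = 1/3, a true prolongation of 10 ms (400 to 410 ms) and a fall from 100 to 80 bpm. QTcB goes from 400 × 0.60^(-1/6) = 435.5 to 410 × 0.75^(-1/6) = 430.1 ms, a change of -5.4 ms. QTcF, which is QT/RR^(1/3), shows the full +10 ms.

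**Step 4. What a second correction adds.** With no true effect and a fall from 100 to 80 bpm:

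| Exponent b | QTcB change (ms) | QTcF change (ms) |
|---|---|---|
| 1/4 | -24.7 | -7.7 |
| 1/3 | -15.9 | 0.0 |
| 0.40 | -9.3 | +5.8 |
| 1/2 | 0 | +13.9 |

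QTcF has the smaller artefact for the exponents up to 0.40 in this table, and the larger one at 1/2. Neither formula is neutral for every exponent. Disagreement between them is the useful signal, because it shows that rate correction is contributing.

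**Step 5. Can existing tables supply this?** Not fully. The correction is non-linear in RR, so mean QT divided by the cube root of mean RR is not the mean of the per-ECG values. The subject listings do contain what is needed, one ECG at a time.

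**The case against.** The strongest reply is that the plan already shows the ingredients. QT and RR receive the same summaries as QTcB, and sitting heart rate is summarised too. A QTcB shift caused by rate would therefore appear beside an RR shift, and QTcF can be worked out from the listings. This stands. It rules out the reading that QTcB is the only QT measure summarised and keeps the severity low. It does not remove the point, because the per-subject change under a second correction is not tabulated.

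Second, change from pre-dose to post-dose at the same visit is also planned, and a drift over weeks largely cancels there. That stands too. The artefact concerns mainly change from baseline, which in an uncontrolled study is mixed with disease course whichever formula is used.

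Third, a reader might infer that the documents expect heart rate to change. They do not say so. The 120 bpm figure is a condition for starting anti-thyroid drugs, not a forecast, and entry caps free T3 and free T4. The change is a possibility inferred from the entry criteria, the permitted treatments and the study aim.

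Fourth, a reader might infer that the primary endpoint is affected. The safety endpoints in the protocol synopsis and SAP section 3.1 do not name ECG. It is a descriptive safety output under section 15.4, with no formal test and no QTc threshold.

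Fifth, a reader might infer that the Data Monitoring Committee would be misled. The synopsis promises it "Summary ECG data- heart rate, PR interval, QRS width, QT interval and QTc interval", without naming a correction formula. SAP section 5.1 assigns those listings to Data Management under a separate plan that is not among these documents. No conclusion about them follows from section 15.4.

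**Conclusion.** The point holds in a limited form. Bazett is the only QT correction in SAP section 15.4, and in this population change from baseline in QTcB can include a heart-rate component. For the illustrative fall from 110 to 75 bpm the artefact is 0 ms at exponent 1/2, about -27 ms at 1/3 and about -43 ms at 1/4. These figures rest on assumed heart rates, an assumed 400 ms corrected QT and assumed exponents. They are examples, not bounds; in particular, 27 ms is not a ceiling.

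One tempting rule should be avoided: interpreting a QTc change only when both corrections agree. In the masking example QTcB shows -5.4 ms and QTcF shows +10 ms, so that rule would discard the real prolongation.

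Severity is minor. No contradiction or missing data is shown, and no test or sample size depends on this.

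**What to change.** Add to SAP section 15.4 a sixth parameter, QTcF = QT/(RR in seconds)^(1/3), derived for each ECG from the recorded QT and RR. RR is recorded in msec, so divide by 1000 first. Give QTcF the same summaries as the other parameters (observed, change from baseline, change from pre-dose) and include it in the by-subject listing, shown beside QTcB, QT and RR. Add a sentence saying that QTcF supplements QTcB and does not replace it, and that where the two differ, the individual QT and RR values will be examined.

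The cost is one derived variable, a few table rows and one listing column. No new data are needed, so this is a free improvement.
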